Moderate vs. Deep Procedural Sedation with Propofol in the Emergency Department

Background:

Providing appropriate analgesia and sedation for the management of pain and anxiety to a diverse group of patients has become a commonplace procedure in the ED. Adequate pain control and alleviation of anxiety improves quality of care and patient satisfaction. Numerous studies have found that PS in the ED is safe, and when properly administered, the incidence of reported complications, including clinically significant respiratory depression, is rare.

Propofol is an anesthetic agent frequently used for PS in the ED and produces sedation, hypnosis, and amnesia, but lacks analgesic properties. In studies conducted at HCMC, we have found that patients are unable to recall whether or not they experienced pain during the procedure when sedated with propofol. There is the possibility that certain parts of the procedure can be later recalled by the patient. If extensive parts of the procedure can be recalled, then this is not an effective sedation.

Previous studies on memory have utilized both images and words as prompts.[1] Research has shown that many people can recall pictures more easily than words.[2] Therefore, using images as prompts could be a more sensitive way to detect whether patients are forming a memory during sedation. A previous study on sedation at HCMC used verbal prompts, and so the feasibility of using images during sedations needs to be assessed.[3] For the pilot portion of this study, a verbal memory assessment will also be performed to ensure that the visual memory assessment is an effective way to assess memory during procedural sedation. If this method of assessing memory is feasible and efficacious, then the randomized phase of the study will commence with using the visual memory assessment alone.

It is unknown whether moderate sedation can decrease respiratory distress while maintaining adequate amnesia. This question was previously asked in another study at HCMC where pre-sedation targets of moderate or deep sedation were assigned. However, there was not adequate separation of the two arms of the study and the sedation target was achieved for only 69.4% of the deep sedation group and 53.8% of the moderate sedation group.[4] Given the lack of separation of the two subject groups, further investigation is required. This study will randomize 150 patients to moderate or deep sedation. The physician will continuously monitor the patient's level of responsiveness to reach the appropriate level of sedation, and will report the achieved depth of sedation following the procedure.

Methods:

The pilot phase will be a prospective, observational study of the feasibility of the use of a visual memory assessment test during PS in the ED. The second phase will be a prospective, randomized study of the relative amnesia and respiratory distress in patients receiving either moderate or deep sedation with propofol. Patients who present to the ED requiring PS who are 18 years of age or older, are able to provide informed consent, and meet criteria for ASA class I or II are eligible for enrollment into the study. Patients will be excluded if they have a known hypersensitivity or contraindication to propofol, are pregnant, are a prisoner, or are unable to give informed consent for any reason, including having clinical evidence of intoxication. During the randomization phase of the study, the patient will be

randomized to moderate or deep sedation after informed consent is obtained. During the pilot study, a baseline memory assessment will be performed by showing the patient one image every 30 seconds for 10 minutes. The patient will be asked to verbalize what the image shows at the time of presentation. During the pilot phase, the patient will also be read a word every 30 seconds and asked to repeat it. Then, the researcher ask the patient which images and words they can recall after 10 minutes; after this, the patient will be shown images in groups of three and asked to pick which image they were shown.

Prior to the procedure, patients will be placed on monitors, per standard of care for ED PS. During the randomized phase, visual prompts will be shown every 30 seconds during the 5 minutes before propofol is given. Baseline measurements will then be obtained. Every 30 seconds during the procedure, data will be recorded and an image will be shown. The patients will be asked to verbalize what the image shows. For the pilot phase, a word will be read every minute and the patient will be asked to repeat it. The patient will be monitored during the procedure by a physician. After the procedure, the physician will record whether moderate or deep sedation was achieved. The patient's recollection after the procedure will be tested with both free recall and recognition in the same manner as the baseline memory test. Also, patients will be asked to score three separate 100 mm visual analog scales in relation to perceived pain during the procedure, recall of the procedure, and overall satisfaction with the procedure.

In addition, during the procedure, all events including drug dosing, interventions, procedures, and adverse events, will be time stamped in the end tidal CO₂ monitor.

Inclusion criteria:

All patients 18 years and older who will undergo procedural sedation in the ED with propofol; procedures requiring sedation include, but are not limited to: fracture reduction, dislocation reduction, cardioversion, incision and drainage, or chest tube placement.

Exclusion criteria:

Known contraindication or allergy to propofol

Unable to give informed consent for any reason, including having clinical evidence of intoxication

Have a chronic medical condition that is currently unstable, or are currently critically ill (ASA Class III or IV)

Are pregnant

Data collection will be performed by trained RAs and will include:

Indication for procedural sedation

Presumed ED diagnosis

Patient demographic information

ED vital signs including pulse, blood pressure, respiratory rate, oxygen saturation, end tidal carbon dioxide

Objective Assessment of Alertness Scale (OAAS) score during the procedure

Interventions during procedure (i.e. bag valve mask use, airway repositioning).

Answers to visual and verbal memory assessment pre-test and post-procedure test

Ability of a patient to verbalize image content during the procedures

Ability of a patient to repeat a word during the procedure

Medications administered or prescribed

Total time of procedure

Procedure outcome (successful or unsuccessful)

Physician rating of procedure difficulty

Patient perception of perceived pain during the procedure, memory of the procedure, and overall satisfaction with the procedure

Data Analysis

The primary outcome of the study is procedural recall. There is currently insufficient data to determine the accuracy or precision of the primary outcome measure, procedural recall as measured by the memory assessment. The first phase of this study will determine the distribution of this measure in the groups and will be used to perform a power analysis for a subsequent trial.

Secondary outcomes will include: adverse respiratory events, defined as any intervention during the procedure in the setting or apnea as measured by end tidal CO₂ or an oxygen saturation of <93%, time of the procedure, success of the procedure, defined as complete procedure in the absence of recall or an adverse respiratory event, patient pain with the procedure, and patient satisfaction.

Data from the end tidal CO₂ monitor will be downloaded in 20 us increments. This deidentified data will be pooled with investigators at three other institutions in order to study waveform changes at the time of events during the procedure.

References:

- [1]: Kawaii H et al. Intravenous sedation for implant surgery: Midazolam, butorphanol and dexmedetomidine versus midazolam, butorphanol and propofol. *J Oral Implantol*. 2011 Dec 29. Epub.
- [2]: Paivio A et al. Free and serial recall of pictures, sounds, and words. *Memory & Cognition*. 1975; 2(6):586-590.
- [3]: Miner JR et al. Assessment of the onset and persistence of amnesia during procedural sedation with propofol. *Acad Emerg Med*. 2005 Jun; 12(6):491-6.

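### Does the lack of a named recall score, and of a chance level for the one-of-three image pick, undermine the primary outcome?

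*Combined protocol and SAP*

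**What the plan says.** All references are to the combined protocol and SAP.

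- **Data Analysis, primary outcome.** The endpoint is "procedural recall as measured by the memory assessment". The same paragraph admits that the measure's accuracy and precision are not yet known, and says the first phase "will determine the distribution of this measure in the groups and will be used to perform a power analysis for a subsequent trial".
- **Methods, test format.** In the pilot baseline test the patient first says what they remember, and then "the patient will be shown images in groups of three and asked to pick which image they were shown". After the procedure, "recollection after the procedure will be tested with both free recall and recognition in the same manner as the baseline memory test", so the same two-part format feeds the primary outcome.
- **Methods, number of items.** "Every 30 seconds during the procedure, data will be recorded and an image will be shown". The number of test items therefore follows the length of the procedure, which is not given.
- **Methods, patient-reported scale.** Patients also complete "three separate 100 mm visual analog scales in relation to perceived pain during the procedure, recall of the procedure", plus a satisfaction scale.
- **Data Analysis, secondary outcomes.** The list includes "time of the procedure, success of the procedure, defined as complete procedure in the absence of recall or an adverse respiratory event". It does not say which recall measure decides that condition.
- **Background.** "If extensive parts of the procedure can be recalled, then this is not an effective sedation". No cut-off is attached to this.

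**The concern.** Three measures could each be called recall: the free-recall count, the recognition pick and the 100 mm scale. The plan does not say which is primary, how it is scored or how the arms are compared. The success outcome depends on the same undefined term.

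The recognition pick adds a further worry. One choice from three can be right by luck about a third of the time, and no reference level is given. If raw picks became the score, a completely amnesic group would appear to remember about 33% of the images. That would matter because the Background speaks of amnesia in absolute terms. If any correct pick ruled out a recall-free procedure, almost no patient with a long procedure could qualify, and an arm with longer procedures would look worse for no reason of memory. The pilot's power analysis also needs a defined score before its distribution can be described.

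**Working it through.** The plan gives no score, chance level or power figure to reproduce, so the check asks what guessing would do under each plausible scoring choice.

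**Inputs.** From Methods: three images per group and one image every 30 seconds. From Background: 150 randomized. Assumed: one target per group with equally plausible distractors, an answer each time, equal allocation (75 per arm), and procedures of 1 to 10 minutes (2 to 20 images).

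**1. Free recall as the score.** There are no options to choose between, so the 1/3 floor does not exist.

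**2. Proportion of picks correct.** With true memory rate m, the expected proportion correct is m + (1 − m)/3.

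- No memory in either arm: 33.3% in both, difference 0. Guessing creates no false difference.
- True memory 0% vs 20%: 33.3% vs 0.20 + 0.80/3 = 46.7%. The difference is 13.3 points, which is 20 × 2/3.
- Test statistic with 10 images and 75 per arm (750 picks per arm, binomial item noise only): SE = √[(0.3333 × 0.6667 + 0.4667 × 0.5333)/750] = 0.0251, so z = 0.1333/0.0251 = 5.32.
- After the correction (proportion − 1/3)/(2/3), the difference and its SE are both multiplied by 3/2, so z is still 5.32. The correction changes the scale and adds no power.

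**3. Any correct pick counted as recall.** The plan states no such rule. A fully amnesic patient would be free of recall with probability (2/3)^N:

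| Images N | Free of recall | Of 75 |
|---|---|---|
| 2 | 44% | 33.3 |
| 5 | 13% | 9.9 |
| 10 | 1.7% | 1.3 |
| 20 | 0.03% | 0.02 |

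If every patient in both arms is fully amnesic, all patients in an arm see the same number of images, and the arms differ by one minute, a two-sided Fisher exact test at 0.05 rejects in 88% of trials at 2 vs 4 images, 40% at 4 vs 6, and 0.1% at 10 vs 12. The large figure belongs to procedures of one versus two minutes. By five versus six minutes it has vanished.

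**4. Unequal declining.** Methods asks patients to pick and mentions no option to decline. If 10% vs 30% of groups were nevertheless declined and scored as wrong, two arms with no memory would read 0.90/3 = 30.0% and 0.70/3 = 23.3%. Both the decline rates and the scoring rule are assumed.

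**5. Would fixing the success rule on free recall cure the dependence on length?** Take 5% recall per image in both arms. The chance of recalling none is 0.95^N: 90%, 77%, 60% and 36% at 2, 5, 10 and 20 images. With the same Fisher test, a one-minute difference gives p < 0.05 in 26% of trials at 2 vs 4 images, 16% at 4 vs 6 and 9% at 10 vs 12. At 10 vs 12 images that is worse than the 0.1% in step 3. Any all-or-none rule varies with the number of images, so this substitution would not remove the problem.

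**The case for a change.** The strongest case for a change is that a primary outcome should have one named score before data are seen. Here the choice among free recall, recognition and a combination is open, so it could be made after looking at results. The pilot does not close this: describing a distribution presupposes a score, and nothing in the plan assigns the choice of score or chance level to the pilot. The recall-free condition in the success outcome is a yes-or-no term, so an any-versus-none reading is natural. Naming the score would take only a few sentences.

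The factual part stands: no section names the score, the between-arm comparison or the chance level, and the success outcome is not tied to a measure. Harm does not follow from that. The plan keeps free recall and recognition apart in words and in administration, and calls the endpoint recall, which can fairly be read as the part with no guessing floor. If recognition is used, the randomized phase is described as a study of relative amnesia, and step 2 shows that comparison is not biased under no difference. The absolute reading would be affected, but the plan sets no threshold against which it could pass or fail. The serious distortions in steps 3 and 4 each need a rule or a decline rate that the plan does not contain.

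**Conclusion.** No change follows. The plan leaves a detail unstated; it does not prescribe a scoring rule that gives a wrong answer. An analyst can see from the format that the pick has a chance level of 1/3, can report free recall and recognition separately because they are collected separately, and would not take one lucky pick as evidence of memory.

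Under a proportion-correct score with similar guessing in both arms, the consequence is a change of scale: 0% memory reads as about 33%, a 20-point difference reads as 13.3 points, and the test statistic is the same with or without correction. Fixing the success outcome on free recall would be a choice of construct for the investigators, and it would still depend on the number of images.

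This rests on one target per group, plausible distractors, and similar guessing and declining in the two arms. It would not hold if any single correct pick were counted as recall, or if declined groups were scored as wrong and declining differed by arm. The plan states neither. The image counts, memory rates and decline rates used above are illustrative.

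### The plan does not provide for keeping the allocation from patients or the research assistants, although free recall, pain and satisfaction are open to expectation or scoring bias

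*Combined protocol and SAP*

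**What the plan says.** The Background sets the size and the comparison: "This study will randomize 150 patients to moderate or deep sedation". It also makes clear that the treating physician must know the target: "The physician will continuously monitor the patient's level of responsiveness to reach the appropriate level of sedation".

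Under Methods, the patient is "randomized to moderate or deep sedation after informed consent is obtained", that is, while awake. The same section says of the main measurement: "The patient's recollection after the procedure will be tested with both free recall and recognition". Recognition means picking the shown image from a group of three. Also under Methods, "patients will be asked to score three separate 100 mm visual analog scales", covering pain, recall and satisfaction.

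The data-collection list opens with "Data collection will be performed by trained RAs and will include". Among its items are "Answers to visual and verbal memory assessment pre-test and post-procedure test" and "Objective Assessment of Alertness Scale (OAAS) score during the procedure", along with interventions, medications and the patient's ratings.

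Data Analysis names procedural recall, as measured by the memory assessment, as the primary outcome. Pain and satisfaction are secondary. Procedure success is also secondary, and its definition requires that there be no recall. The recall scale is collected but is not named as an outcome.

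Blinding, masking and allocation concealment are not mentioned anywhere.

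**The concern.** The person who titrates sedation has to know the arm. The patient and the RA do not. A patient who knows that the target was moderate or deep may rate pain and satisfaction to match. An RA who knows the arm may prompt more or less, or be more or less generous in accepting a free-recall answer. The plan gives no script and no scoring key for that judgement.

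The consequence reaches beyond the primary outcome. Success requires the absence of recall and no threshold is given, so one accepted answer could also change a patient's classification on that secondary outcome. An arm difference produced in this way could not be separated afterwards from a real effect of sedation depth on memory.

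**Working it through.** **1. Who needs the allocation and who could influence an outcome**

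| Role | Needs the target? | Outcome it can influence | Protection stated |
|---|---|---|---|
| Treating physician | Yes, to titrate | Achieved depth | Not possible |
| Patient | No | Pain and satisfaction scales; effort in the recall test | None |
| RA | No | Free recall, by prompting or by accepting answers | None |

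Exposure differs by measure. Choosing one image from three is largely objective. Free recall is the exposed part of the primary outcome. The scales depend mainly on the patient.

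**2. The plan's own figure.** The 150 cannot be reproduced, because no significance level, power, effect size or SD is given. Everything below illustrates sensitivity under assumptions and does not predict bias.

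**3. Detectable difference.** Assume 1:1 allocation (75 per arm), two-sided 0.05 and 80% power:

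(1.960 + 0.842) × √(2/75) = 0.457 SD.

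- SD of 10 recall points (assumed): 0.457 × 10 = 4.6 points.
- SD of 30 recall points (assumed): 0.457 × 30 = 13.7 points.

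**4. Weight of one credited image.** Images are shown every 30 seconds. The plan gives no procedure length. If it is 10 minutes (assumed), 20 images are shown. The 5-minute lead-in in Methods adds 10, giving 30 if those are scored too.

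- 20 images: 1/20 = 5 points.
- 30 images: 1/30 = 3.3 points.

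As a share of the detectable difference, this runs from 3.3/13.7 = 24% to 5/4.6 = 109%. A shift of that size between arms would require every patient in one arm to be miscredited by one image and none in the other.

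**5. Effect of a shift on a 100 mm scale.** Assume no true difference, a 5 mm shift between arms from knowledge of the allocation, and SE = SD × √(2/75).

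| SD (assumed) | SE | False-positive rate |
|---|---|---|
| 20 mm | 3.27 mm | 33% |
| 25 mm | 4.08 mm | 23% |
| 30 mm | 4.90 mm | 18% |

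**6. What an untold RA could still infer.** The Background reports that an earlier study at the site reached the target in 69.4% of the deep group and 53.8% of the moderate group. Assume 1:1 allocation and that patients who missed one target reached the other. An RA who guesses the arm from observed depth is then right in (0.694 + 0.538)/2 = 61.6% of patients, against 50% by chance.

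The difference between arms in the share believed deep is 0.694 − (1 − 0.538) = 0.232. If that guess were the only route, a 5 mm shift would shrink to 0.232 × 5 = 1.16 mm. The false-positive rate would be about 6% to 7% over the same SDs. Better separation of the arms, which this trial seeks, would raise the guess rate.

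**The case against.** The strongest reply is that silence is not a defect of conduct. The document does not say that patients are told their arm, and the consent text, which could settle this, was not available for review. A reader might infer that patients are told moderate or deep, or that one RA shows the images, scores sedation, runs the recall test and judges the answers. Neither inference is supported: randomization is only said to follow consent, and staffing is not described. This part of the objection stands.

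It is also fair to say that exposure is limited. Recognition leaves little to judgement. Patients name each image when shown, which gives a reference for later matching when they can respond. The recall scale is not a named outcome. No direction of staff expectation can be assumed, since the Background calls it unknown whether moderate sedation maintains amnesia. These points narrow the concern to free recall, pain and satisfaction. They do not remove it, because free recall is part of the primary outcome.

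Finally, RAs who record sedation depth, interventions and medications cannot be fully blinded. A reader might infer that the bias can be prevented without extra staff. The documents do not show that. A fully blinded tester would have to be absent from the sedation, and nothing says that such a person is available. Partial blinding is still worth having: the patient simply need not be told, and later coded scoring can separate the scorer from both the arm and the observed depth.

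**Conclusion.** The concern holds in this limited form: the plan contains no provision to keep the allocation from patients or RAs, and this leaves free recall, pain and satisfaction open to expectation or scoring bias. It should be corrected, because the safeguard is cheap and changes neither the sedation targets nor the sample size.

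Its size is unknown. A reader might take the per-image figure as showing that lenient scoring would use up most of the detectable effect. The documents do not support this. The result depends on assumed allocation ratio, image count and SD, and on uniform miscrediting in one arm only. Data Analysis itself says that the accuracy and precision of the recall measure are not yet known. The 62% guess rate rests on the earlier study's separation of arms and on the two assumptions given with it.

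**What to change.** - **Allocation.** State that only the treating physician receives it. Patients and RAs are not told it until the memory test and scales are complete. When the physician opens it need not be tied to the lead-in images.
- **Free recall.** RAs give the test from a fixed script and write answers word for word.
- **Scoring.** Score the answers later against the list of images shown, with a preset key, on sheets carrying only the study number. The scorer should preferably not have attended that sedation, since the code otherwise hides little.
- **Optional.** Preset the recognition triplets by study number.

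The cost is a concealed allocation for the physician, a sentence in the consent text, coded sheets and a little later scoring work. That work is assumed to fall to existing staff, which the sponsor should confirm. The remaining limitation is that RAs at the bedside see sedation depth and are only partly blinded. The plan should say so.

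### Does fixing 150 patients with no stated basis, and no allowance for overlap between the sedation arms, require a change to the plan?

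*Combined protocol and SAP*

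**What the plan says.** The Background announces the size in one sentence: "This study will randomize 150 patients to moderate or deep sedation". No significance level, power, effect, variance, event rate, margin, dropout allowance or allocation ratio appears anywhere.

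The Data Analysis section names procedural recall as the primary outcome and says its accuracy and precision cannot yet be judged. The first phase "will determine the distribution of this measure in the groups and will be used to perform a power analysis for a subsequent trial". Neither the groups nor the subsequent trial is defined. The Background's only condition for moving on concerns the memory test: "If this method of assessing memory is feasible and efficacious, then the randomized phase of the study will commence".

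On separation, the Background says that in the earlier study "the sedation target was achieved for only 69.4% of the deep sedation group and 53.8% of the moderate sedation group", and concludes: "Given the lack of separation of the two subject groups, further investigation is required". The design response is that the physician watches responsiveness continuously in order to reach the intended level and reports the depth achieved. The data collection list adds the alertness scale (OAAS) score during the procedure. The clinical question is stated as: "It is unknown whether moderate sedation can decrease respiratory distress while maintaining adequate amnesia".

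**The concern.** Three things look wrong together.

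- **No basis for 150.** The number is fixed in a document that says the inputs needed to justify it do not exist.
- **No link to the pilot.** If the subsequent trial is the randomized phase, 150 was set before the analysis meant to set it. If it is a later trial, 150 has no power or precision statement at all.
- **No allowance for overlap.** The plan names poor separation as its reason for asking the question again, but assumes no separation and carries none into the sample size. The pilot is described thus: "The pilot phase will be a prospective, observational study of the feasibility of the use of a visual memory assessment test". It assigns no arms, so the groups in the Data Analysis sentence are most plausibly achieved depths. A recall difference by achieved depth would be larger than one by assigned arm whenever some patients miss their target.

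The stake is the reading of the primary outcome. Arms that overlap in depth will look alike on recall, and similarity is the result that would favour moderate sedation. With no margin or reading rule, a non-significant difference could be mistaken for evidence that amnesia was maintained.

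**Working it through.** **Can 150 be reproduced?** No, because none of the inputs is stated. Several assumed sets come close: by the normal approximation at 80% power, 0.457 SD gives 152 in total, and recall of 5% versus 20% also gives 152. Others do not: 10% versus 20% gives 398. The number can be neither confirmed nor refuted.

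**What 150 delivers.** Assumed: 75 per arm, two-sided 5%.

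- Detectable difference at 80% power, two-sample t test: 0.460 SD.
- 95% half-width for a mean difference: 1.96 × √(2/75) = 0.320 SD.
- 95% half-width for yes/no recall, 1.96 × √(2p(1−p)/75): 7.0, 9.6 and 12.8 points at p = 5%, 10% and 20%.

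**What overlap would cost.** Assume recall depends only on achieved depth and the arms are compared as assigned. Let c be the share of misses that land at the other depth, the rest having their target's recall. The earlier study's misses were 100 − 69.4 = 30.6% (deep) and 100 − 53.8 = 46.2% (moderate). Separation is s = 1 − c × (0.306 + 0.462), and the as-assigned difference is s times the difference by achieved depth. Power below is for 0.460 × s at 75 per arm, with the arm SD held fixed.

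| Scenario | s | 1/s | Power |
|---|---|---|---|
| Full separation | 1.00 | 1.00 | 80% |
| 90% on target in both arms, c = 1 | 0.80 | 1.25 | 61% |
| 80% on target in both arms, c = 1 | 0.60 | 1.67 | 39% |
| Earlier rates, c = 0.25 | 0.808 | 1.24 | 62% |
| Earlier rates, c = 0.5 | 0.616 | 1.62 | 41% |
| Earlier rates, c = 0.75 | 0.424 | 2.36 | 22% |
| Earlier rates, c = 1 | 0.232 | 4.31 | 10% |

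The documents do not say what depth the earlier misses reached, so c is unknown and the last row is a bound, not an estimate.

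**A figure not to rely on.** One can also ask what difference D, in within-depth SD units, 150 could detect in that last row, allowing for the extra spread from mixed depths. This solves s·D/√(1 + v·D²) = 0.460, where v is the average of m(1−m) over the arms and m is the share at the other depth. Here v = (0.306 × 0.694 + 0.462 × 0.538)/2 = 0.230, and D is about 6.5. But the left side can never exceed s/√v = 0.232/√0.230 = 0.483, barely above 0.460. Lower both target rates by half a point and D is about 35; lower them by one point and there is no solution. The 6.5 says nothing useful about the trial.

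**Would a sizing step between phases help?** The natural proposal is to multiply the pilot's recall difference by the pilot's separation, and to treat the randomized comparison as estimation only if power at 150 is below 80%. The documents give no pilot size. With 40 patients split evenly (assumed), the difference carries ±1.96 × √(2/20) = ±0.62 SD, and a separation of 0.60 from 80% achievement carries ±1.96 × √(2 × 0.8 × 0.2/20) = ±25 points. Take an assumed pilot difference of 0.8 SD with separation 0.60: the as-assigned difference is 0.48 SD and power is 83%. Move only the pilot difference across its interval, 0.18 to 1.42 SD, and power runs from 10% to over 99%. Such a trigger would fire or not largely by chance.

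**The case for a change.** The strongest case for a change is that the plan identifies its own failure mode and then ignores it in the sample size. This does not depend on the worst case: 90% achievement in both arms, with all misses crossing over, already takes nominal 80% power to 61%. The lack of a basis for 150 holds however the subsequent trial is read, and clearer wording would cost little before randomization starts.

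The facts in that argument stand. The inference that the plan must change is weaker.

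- **The overstatement corrects a calculation the plan does not contain.** It needs the groups to mean achieved depth, the subsequent trial to mean the randomized phase, comparison as assigned, recall driven by depth alone, and misses that cross over. The Data Analysis section states none of these, and the Methods speak only of relative outcomes "in patients receiving either moderate or deep sedation with propofol". If a later trial is meant, the pilot analysis never sizes 150 and nothing about 150 is overstated.
- **Separation is addressed by design.** Continuous monitoring towards the target is aimed at the earlier problem. No achievement rate is promised for it, so it is not a sample-size allowance, but the overlap has not been overlooked.
- **Pilot separation is a poor substitute.** In an observational pilot the physician chooses the depth for each patient. Success at a self-chosen depth need not carry over to an assigned target and could well be higher. The earlier rates are the documents' only data under assigned targets.
- **An interval by assigned arm does not cure the stated harm.** It is diluted by the same overlap. What helps the reader is the separation achieved in the randomized phase, and the physician-recorded depth and OAAS scores needed for that are already collected.

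**Conclusion.** No change to the plan follows. The 150 has no stated basis, the pilot's power analysis is not tied to it, and no expected separation enters it. These are omissions of detail, not errors that would produce a wrong result: the plan makes no power or precision claim that 150 misses, says openly that recall data are insufficient, and sets no rule by which a non-significant difference would be read as preserved amnesia. That misreading is a risk in interpretation, not something the plan says it will do.

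A competent analyst fills the gap from what is collected: recall compared by assigned arm with a confidence interval, achieved separation shown beside it from the recorded depth and OAAS, and no claim of maintained amnesia from non-significance alone. The expected precision is about 0.32 SD, or 7 to 13 points for yes/no recall of 5% to 20%, assuming 75 per arm and a two-sided 5% level. The possible loss of power, from 80% to about 61% or 39% at 90% or 80% achievement with all misses crossing over, is a sensitivity range that rests on comparison as assigned and on recall depending only on achieved depth. The one substantive addition on offer, a power trigger based on the pilot, would rest on inputs too imprecise and too poorly matched to assigned targets to improve the trial.
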